#### 5.1.2 Laboratory Evaluations

##### 5.1.2.1 *Table: Clinical Laboratory Tests (validated tests performed in a CLIA/CAP lab)*

Category	Tests
Hematology	Hemoglobin, hematocrit, platelet count, WBC with differential
Liver function tests	SGOT/AST, SGPT/ALT, total Bilirubin
Renal function tests	BUN, creatinine
Blood gas	PaO 2 , PaCO 2

### 5.2 Efficacy Evaluations

The primary outcome (Aim 1A) of PARMA is time to sustained resolution of hypoxemia, defined as being alive with PaO2/FIO2 > 300 (or SpO2/FIO2 > 315) on two consecutive measurements 4 hours apart. This is because improved oxygenation is strongly associated with outcome in pediatric ARDS, and is the most plausible mechanism for the efficacy of a high ΔP strategy, both for composite outcomes such as VFDs (by shortening invasive ventilator duration and avoidance of rescue therapies), as well as mortality (improved organ function via improved gas exchange and reduced morbidity associated with prolonged ventilation). This outcome is censored at 28 days (672 hours).

### 5.3 Safety Evaluation

Adverse events (AEs), whether anticipated or unanticipated, will be recorded according to the date of first occurrence, severity, and their duration. Notably, ARDS is a life-threatening condition for which we expect a wide range of events as part of the routine clinical course. Secondary Safety Endpoints include: pneumothorax requiring chest tube; acidosis requiring additional vasopressor support; protocol termination for failure criteria; other air leak not requiring chest tubes. Ventilator-

associated pneumonia; new or progressive multiple organ dysfunction syndrome are being recorded as secondary aims, and also serve as potential safety outcomes.

## 6 STATISTICAL CONSIDERATIONS

### 6.1 Primary Endpoint

The primary outcome (Aim 1A) of PARMA is time to sustained resolution of hypoxemia, defined as being alive with  $\text{PaO}_2/\text{FIO}_2 > 300$  (or  $\text{SpO}_2/\text{FIO}_2 > 315$ ) on two consecutive measurements 4 hours apart. This is because improved oxygenation is strongly associated with outcome in pediatric ARDS, and is the most plausible mechanism for the efficacy of a high  $\Delta P$  strategy, both for composite outcomes such as VFDs (by shortening invasive ventilator duration and avoidance of rescue therapies), as well as mortality (improved organ function via improved gas exchange and reduced morbidity associated with prolonged ventilation). This outcome is censored at 28 days (672 hours).

### 6.2 Secondary Endpoints

The secondary endpoints are:

- Lung aeration determined by pre- versus post-randomization EIT
- VFDs at 28 days
- New oxygen- or ventilator-dependency at discharge
- Mortality at 28 days, PICU discharge, and hospital discharge
- Safety Endpoints listed above in section 5

### 6.3 Statistical Methods

#### 6.3.1 Baseline Data

Baseline and demographic characteristics will be summarized by standard descriptive summaries (e.g. means and standard deviations for continuous variables such as age and percentages for categorical variables such as gender).

#### 6.3.2 Efficacy Analysis

PARMA will be analyzed using Bayesian survival analyses, with effect size presented as a hazard ratio (HR). All analyses will be “intention to treat.” The main analysis will use a minimally informative prior centered at  $\text{HR} = 1$  ( $\log[\text{HR}] = 0$ ) and precision = 10 (log scale). The primary outcome of hypoxemia resolution (Aim 1A) will be assessed as a time to event (in hours) from randomization until the primary event of hypoxemia resolution. Subjects who die before hypoxemia resolution will remain in the risk set and be considered as being “never able to achieve hypoxemia resolution” (effectively being treated as a competing risk). Subjects who achieve hypoxemia resolution and die subsequent to that will be considered as having achieved the primary outcome. The high  $\Delta P$  (comparator) arm will be compared to the low  $\Delta P$  (reference) arm, and efficacy reported as HR with 95% credible intervals. Posterior probabilities under minimally informative priors will be computed for any benefit ( $\text{HR} > 1$ , meaning faster time to hypoxemia resolution with high  $\Delta P$ ),

HR > 1.25, and HR > 1.5 (projected “true” effect size). Additional analyses will be conducted with standardized priors reflecting pessimistic (priors centered at HR 0.8) and optimistic (priors centered at HR 1.2) scenarios, as we have done before. As this is the first trial of different  $\Delta P$  ventilation strategies on hypoxemia resolution in pediatric ARDS, reasonable data-driven priors from previous publications, including adult trial data, were not available. The standardized prior framework (minimally informative, pessimistic, optimistic) reflects a range of plausible priors with the same precision under which the PARMA trial data can be adjusted to derive posterior probabilities.

For Aim 1B, we will assess whether the effect size of high versus low  $\Delta P$  ventilation differs according to age (continuous in years and as strata of < 1 year, 1 to < 5 years, 5 to < 12 years, and 12 to 18 years), pre-randomization elastance ( $\Delta P/V_T$  with  $V_T$  normalized to IBW), and pre-randomization  $\text{PaO}_2/\text{FIO}_2$ .

For Aim 2, pre- and post-randomization EIT images (in the immediate 8 hours after randomization) will be used to determine the change in aeration. Lung images will be divided into 4 ROIs along the axial and sagittal planes, and impedance (i.e., aeration) will be determined for each region. Post-randomization end-expiratory lung impedance (EELZ) values and elastance (measured at the ventilator) will be compared to pre-randomization to determine whether ventilator changes results in recruitment (increased EELZ; unchanged or improved elastance), overdistension (increased EELZ; worsened elastance), or atelectasis (decreased EELZ; worsened or unchanged elastance). This analysis will be repeated with the second set of post-randomization EIT measurements (performed 24 to 72 hours after randomization), again compared to pre-randomization EIT. We will compare the proportion of subjects with improved recruitment and with overdistension, relative to pre-randomization EIT, between high and low  $\Delta P$  arms, with effect sizes presented as relative risk (RR). RR > 1 implies a greater proportion of subjects with the reported aeration (e.g., recruitment) with high  $\Delta P$ .

We will compute the posterior probability under minimally informative priors for any benefit when comparing 28-day mortality, PICU mortality, and hospital mortality between high and low  $\Delta P$  arms. Effect sizes will be presented as RR, with RR < 1 meaning lower mortality risk with high  $\Delta P$ . Additional analyses will be conducted with standardized priors reflecting pessimistic (priors centered at RR 1.2) and optimistic (priors centered at RR 0.8) scenarios, and with data-driven priors using effect sizes from prior adult  $V_T$  trials, including ARMA.

Analyses of VFDs and other free-day clinical endpoints will be conducted as described above for hypoxemia resolution, with death prior to the main event being treated as a competing risk and effect sizes presented on the HR scale with HR > 1 meaning superiority of high  $\Delta P$  ventilation. The main analyses will be conducted using minimally informative priors (as per main analysis), with additional analyses conducted using standardized priors reflecting pessimistic (priors centered at HR 0.8) and optimistic (priors centered at HR 1.2) scenarios, and with data-driven priors using effect sizes from prior adult  $V_T$  trials.

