Statistical And Analytic Plan	PARMA will be analyzed using Bayesian survival analyses, with effect size presented as a hazard ratio (HR). The main analysis will use a minimally informative prior centered at $HR = 1$ ( $\log[HR] = 0$ ) and precision = 10 (log scale). The primary outcome of hypoxemia resolution (Aim 1) will be assessed as a time to event (in hours) from randomization until the primary event of hypoxemia resolution. Subjects who die before hypoxemia resolution will remain in the risk set and be considered as being “never able to achieve hypoxemia resolution” (effectively being treated as a competing risk). Subjects who achieve hypoxemia resolution and die subsequent to that will be considered as having achieved the primary outcome. The high $\Delta P$ (comparator) arm will be compared to the low $\Delta P$ (reference) arm, and efficacy reported as HR with 95% credible intervals. Posterior probabilities under minimally informative priors will be computed for any benefit (HR > 1, meaning faster time to hypoxemia resolution with high $\Delta P$ ), HR > 1.25, and HR > 1.5 (projected “true” effect size).

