## 3.4 Study Population

Eligibility criteria were designed to enroll children with Berlin-defined ARDS without limitations of care and expected to survive > 72 hours in the CHOP PICU. We specifically chose Berlin criteria rather than the 2015 or 2022 PALICC pediatric ARDS criteria for two reasons. First, the PALICC defines ARDS severity using oxygenation index, rather than  $\text{PaO}_2/\text{FIO}_2$ , which incorporates mean airway pressures (mPaw). However, the high  $\Delta P$  arm in PARMA will have higher mPaw (by definition), and the Berlin definition (using  $\text{PaO}_2/\text{FIO}_2$ ) may be a more reliable metric of hypoxemia severity and resolution. Second, PALICC has less restrictive radiographic criteria (unilateral opacities allowed), and so we anticipate all subjects with Berlin ARDS in PARMA would also meet criteria for the PALICC definition of pediatric ARDS.

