### **3.4.1 Inclusion Criteria (examples)**

- 1) age > 2 weeks (> 38 weeks corrected gestational age) and < 18 years (not yet had 18th birthday)
- 2) acute ( $\leq$  7 days of inciting etiology) respiratory failure requiring invasive mechanical ventilation
- 3) ventilated with endotracheal tube or tracheostomy for  $\leq$  7 days from inciting etiology (e.g., pneumonia, sepsis, trauma, aspiration, cardiac arrest, pancreatitis, engineered T cell therapy, among others) onset
- 4) hypoxemia defined as  $\text{PaO}_2/\text{FIO}_2 \leq 300$  (or  $\text{SpO}_2/\text{FIO}_2 \leq 315$ ) on  $\text{PEEP} \geq 5 \text{ cmH}_2\text{O}$  on two consecutive measurements 4 hours apart and sustained at the time of consent and randomization
- 5) bilateral opacities on chest radiograph as determined by radiologist, clinical attending, or PI

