## 5 STUDY EVALUATIONS AND MEASUREMENTS

### 5.1 Screening and Monitoring Evaluations and Measurements

#### 5.1.1 Medical Record Review

Detailed clinical data will be recorded, including demographics (age and sex), severity of illness (Pediatric Risk of Mortality [PRISM] IV; Pediatric Logistic Organ Dysfunction [PELOD] 2), co-morbidities (prematurity, immunocompromised status, stem cell transplant), and ARDS etiology (e.g., pneumonia, sepsis, trauma, aspiration). Pre- and post-randomization ventilator settings, oxygenation, ancillary therapy use, and adverse events will be documented daily until discontinuation of invasive ventilator support. Organ failures (PELOD 2 score derived from labs), vasopressor support, and clinical outcomes will be monitored until hospital discharge. REDCap will serve as the data collection interface.

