## **6.4 Sample Size and Power**

Sample size was evaluated using trial simulations. We assumed that time to hypoxemia resolution and competing event followed Weibull distributions, using data from > 1000 pediatric ARDS cases at CHOP between 2011 and 2023 to estimate the shape and scale parameters. Using a projected “true” HR of 1.5 favoring high  $\Delta P$  ventilation, 160 subjects would provide 80% power to detect a  $> 90\%$  probability of any benefit (HR  $> 1$ ) with high  $\Delta P$  at a type I error rate = 0.07 (10,000 simulations) assuming a minimally informative prior (centered at HR = 1 and precision = 10 [log scale]). In this phase 2A trial, we accept 80% power to detect a 90% probability of any benefit at a type I error rate  $< 0.1$  in anticipation of a larger trial.

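### Cheap improvement, not an error: the primary HR is described without a baseline covariate, although pre-randomization oxygenation is already recorded and could add power at the same n and type I error

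*Protocol*

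**What the plan says.** Section 6.3.2 fixes the primary analysis in some detail: a Bayesian survival model, a prior on log HR centered at 0 with precision 10, deaths kept in the risk set, and posterior probabilities for HR above 1, 1.25 and 1.5. The contrast is high against low ΔP, in the words "reference) arm, and efficacy reported as HR with 95% credible intervals". The synopsis has the same sentence, "efficacy reported as HR with 95% credible intervals". Neither place names a baseline covariate. Where 6.3.2 speaks of adjusting, it means combining the data with priors. Sections 3.2 and 9.1.1 describe 1:1 permuted blocks and name no stratification factor.

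Baseline oxygenation is already in the plan in three ways:

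- **Eligibility.** Section 3.4.1 requires PaO2/FIO2 at or below 300 (or SpO2/FIO2 at or below 315) "on two consecutive measurements 4 hours apart and sustained at the time of consent and randomization". Section 6.1 defines the event as the same indices rising above the same cut-offs. Section 3.4 says of the Berlin definition, which uses PaO2/FIO2, that it "may be a more reliable metric of hypoxemia severity and resolution".
- **Data collection.** Section 5.1.1 states: "Pre- and post-randomization ventilator settings, oxygenation, ancillary therapy use, and adverse events will be documented daily".
- **Aim 1B.** The sentence that opens "For Aim 1B, we will assess whether the effect size of high versus low" lists pre-randomization PaO2/FIO2 among the effect modifiers.

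Section 6.4 gives 80% power and type I error 0.07 for 160 subjects and a projected HR of 1.5. It sets the standard as "we accept 80% power to detect a 90% probability of any benefit at a type I error rate" below 0.1.

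**The concern.** The endpoint is the time until an oxygenation index crosses a threshold, and subjects start at different distances below it. A prognostic link between starting value and time to resolution is therefore plausible. If the link exists, a model with arm alone pulls the estimated HR toward 1 and leaves the single trial result open to chance differences in starting oxygenation. Neither the allocation nor the described primary analysis uses this information.

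The stake is efficiency. The trial has one center with about 90 ARDS cases a year (section 9.5), so power gained without more subjects is worth having. The trial is also open-label, so a covariate named in advance carries more weight than one chosen after data have been seen.

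**Working it through.** **1. Reproduce the stated figures.** Inputs from section 6.4: n = 160, HR 1.5, success if P(HR > 1) > 0.90, prior precision 10. The number of events d is not given and is assumed.

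With the log HR estimate distributed N(log HR, 4/d), the rule is met when Z > 1.2816 × √((d/4 + 10)/(d/4)).

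For d = 130 (130/160 = 81%):
- d/4 = 32.5, and the critical value is 1.2816 × √(42.5/32.5) = 1.4655.
- Type I error = 1 − Φ(1.4655) = 0.071.
- Power = Φ(0.4055 × √32.5 − 1.4655) = Φ(0.846) = 0.801.

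At d = 120 and 140, power is 77.1% and 82.8%, and type I error is 0.070 and 0.073. One plausible event fraction thus gives both stated figures for an arm-only contrast.

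**2. Add the covariate.** Trials were simulated with n = 160, permuted blocks of 4, Weibull shape 0.8, 75% resolution in the low arm and deaths held in the risk set to 672 h (about 128 to 130 events). Block size, shape and resolution rate are assumptions. A Cox model with arm alone was compared with arm plus standardized baseline oxygenation, using the same prior on the arm effect and the same 0.90 rule. The prognostic strength (HR per SD) is also assumed.

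| HR per SD | Arm only, 1.5 marginal | Adjusted, 1.5 marginal | Gain (points) | Arm only, 1.5 conditional | Adjusted, 1.5 conditional | Gain (points) |
|---|---|---|---|---|---|---|
| 1.0 | 0.79–0.80 | 0.80 | 0 | 0.80 | 0.80 | −0.2 |
| 1.2 | 0.79–0.80 | 0.80 | 1 | 0.79 | 0.80 | 1 |
| 1.35 | 0.79–0.80 | 0.83 | 3 | 0.77 | 0.80 | 3 |
| 1.65 | 0.79–0.80 | 0.87 | 8 | 0.71 | 0.79 | 9 |
| 2.0 | 0.79–0.80 | 0.92 | 12 | 0.64 | 0.78 | 14 |

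Overall type I error was 0.067 to 0.070 for both models.

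A separate simulation (10,000 trials per cell, about 130 events) agrees. On the marginal reading, power went from 79% to 81% at HR per SD 1.25, 81% to 86% at 1.5, 80% to 89% at 1.75 and 81% to 93% at 2.0. Type I error lay between 0.067 and 0.076, and the two models differed by no more than 0.001 at each of these strengths (Monte Carlo standard error 0.0026).

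**3. Where the gain comes from.** The standard error of the log HR hardly moves: 0.177 arm-only, 0.178 to 0.179 adjusted. What changes is the target. A marginal 1.5 corresponds to a conditional 1.51, 1.53, 1.59 and 1.66 at HR per SD 1.2, 1.35, 1.65 and 2.0.

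Hand check at 1.65, with standard error 0.179:
- Information = 1/0.179² = 31.2, and the critical value is 1.2816 × √(41.2/31.2) = 1.473.
- Power = Φ(log 1.59/0.179 − 1.473) = Φ(2.591 − 1.473) = Φ(1.118) = 0.87, as in the table.

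**4. Event rate.** On the conditional reading, at HR per SD 1.0, 1.2 and 2.0:
- 65% low-arm resolution: 0.760 to 0.757, 0.753 to 0.766, 0.614 to 0.742.
- 85% low-arm resolution: 0.835 to 0.833, 0.821 to 0.832, 0.663 to 0.823.

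The gain does not depend on the 75% assumption.

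**5. Chance imbalance.** With 80 per arm, the between-arm difference in baseline means has SD √(2/80) = 0.158. A difference of at least 0.2 SD has probability 1 − Φ(0.2/0.158), about 10% in each direction. Given such a difference, and with no true effect, the probability of declaring benefit at HR per SD 1.2 / 1.35 / 1.65 / 2.0 is:

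| | High arm starts better | High arm starts worse |
|---|---|---|
| Arm only | 0.10 / 0.14 / 0.20 / 0.23 | 0.04 / 0.02 / 0.01 / 0.005 |
| Adjusted | 0.06–0.08 | 0.06–0.08 |

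**The case against.** The strongest reply is that nothing here is wrong. Covariates for the primary model are commonly left to the SAP, which was not available for this review and may already name them. The Protocol never says that the model is unadjusted; that is inferred from silence, and an HR from a model with covariates would fit the same sentence. An interaction model for Aim 1B would normally contain the main effect of baseline PaO2/FIO2 anyway. A simple arm HR that meets its stated operating characteristics is a legitimate choice for a phase 2A trial. All of this stands, and it is why the point is a suggestion.

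The prognostic strength is also not in the Protocol. Section 3.4 argues about which index to use, and section 6.1 speaks of improved oxygenation and outcome; neither shows that the starting value predicts time to resolution. The baseline is taken at pre-randomization ventilator settings and may be noisy. This stands too, so the size of the gain is conditional on an estimate that the sponsor has yet to make.

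A reader might go further and infer that the trial is underpowered, with power as low as 0.64, or that an arm-only trial would need about 175 or 202 subjects to match the adjusted 160 (HR per SD 1.35 or 1.65). Those figures hold only if 1.5 is a conditional HR. Section 6.4 mentions no covariate, so the natural reading is marginal, and arm-only power is then 0.79 to 0.80 as promised. A reader might also take the 0.14 to 0.23 under imbalance as a breach of the 0.1 limit. It is not: those are probabilities given an unlucky allocation, they are offset by low values in the other direction, and the error over all randomizations stays near 0.07.

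**Conclusion.** The point holds as a low-cost improvement. The stated power and type I error reproduce and are not breached.

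Reading 1.5 as marginal, prespecified adjustment for baseline oxygenation gains about 0 to 1 point at HR per SD 1.0 to 1.2, 3 at 1.35, 8 at 1.65 and 12 at 2.0. Gains are similar if 1.5 is conditional. Type I error stays at about 0.07. Adjustment also removes the dependence of this one result on chance imbalance in starting oxygenation, which is a conditional property only.

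The sizes rest on an assumed prognostic strength, an assumed event fraction near 80%, and a covariate measured without much error. If SpO2-only subjects left the covariate 70% reliable (assumed, conditional reading), the gains at 1.35, 1.65 and 2.0 would be about 2, 5 and 10 points.

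**What to change.** Unless the SAP already does this:

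1. Estimate the HR per SD of baseline oxygenation for time to resolution from the registry that supplied the Weibull parameters (section 6.4: "using data from > 1000 pediatric ARDS cases at CHOP between 2011 and 2023 to estimate the shape and scale parameters"), and re-run the 6.4 simulation with it.
2. State in 6.3.2 that the primary Bayesian survival model includes continuous pre-randomization oxygenation as log PaO2/FIO2, with one prespecified rule for subjects who have only SpO2/FIO2.
3. Report the arm-only HR as a sensitivity analysis.
4. Say that the HR, its priors, the projected 1.5 and the 1.25 and 1.5 thresholds are then conditional on the covariate.

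The cost is a few sentences in 6.3.2 and 6.4, one registry analysis and one simulation re-run, with no new trial data. The downsides are 0.1 to 0.3 power points if the covariate is not prognostic, a reported HR somewhat further from 1 than the marginal one, and the need to write the SpO2 rule before data are seen.

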## 1 BACKGROUND INFORMATION AND RATIONALE

### 1.1 Introduction

ARDS is characterized by acute onset of diffuse bilateral pulmonary edema and severe hypoxemia not fully explained by cardiac dysfunction. Primarily defined for adults, ARDS affects 45,000 children in the United States (US) annually, representing 10% of mechanically ventilated children in pediatric intensive care units (PICUs), with a mortality rate of 20% in the United States and 30% worldwide. Despite several large multicenter trials, there are no specific therapies for adult or pediatric ARDS, and supportive care with lung-protective ventilation and fluid restriction remains the mainstay of treatment. In children, a lack of therapies is further compounded by uncertainty in management, as guidelines are typically extrapolated from adult ARDS, with uncertain applicability. Pediatric ARDS possesses a distinct epidemiology, outcomes, and pathobiology, necessitating studies specific to this population. We have published how the lower mortality rate in children necessitates alternative patient-centered outcomes for interventional trials. Additionally, as risk factors and co-morbidities differ from adult ARDS, the tradeoff between risks and benefits for any given intervention cannot be assumed to directly translate from adults to children. For example, in adult ARDS, prone positioning improved mortality, and inhaled nitric oxide did not affect either mortality or the composite outcome of ventilator-free days (VFDs) at 28 days. By contrast, prone positioning did not affect clinical outcomes in children, whereas inhaled nitric oxide improved VFDs in children.

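### The rule carried over to ventilator-free days counts a child extubated and dead by day 28 as a success, so the VFD hazard ratio misses deaths after extubation

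*Protocol*

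**What the plan says.** The last paragraph of Protocol Section 6.3.2 sets the method for VFDs by cross-reference: "Analyses of VFDs and other free-day clinical endpoints will be conducted as described above for hypoxemia resolution". The same sentence goes on: "with death prior to the main event being treated as a competing risk and effect sizes presented on the HR scale".

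The method referred to is in the first paragraph of that section and has two parts.
- Death before the event: "Subjects who die before hypoxemia resolution will remain in the risk set and be considered as being" never able to reach it.
- Death after the event: "Subjects who achieve hypoxemia resolution and die subsequent to that will be considered as having achieved the primary outcome".

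The VFD paragraph repeats the first part and makes no exception to the second.

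Section 6.2 lists "VFDs at 28 days" as a secondary endpoint and, separately, "Mortality at 28 days, PICU discharge, and hospital discharge". Section 1.1 refers to "the composite outcome of ventilator-free days (VFDs) at 28 days". Sections 5.2 and 6.1 also name VFDs as an example of a composite outcome when they justify the primary endpoint. The protocol gives no other scoring rule for VFDs.

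**The concern.** For hypoxemia resolution, counting the event even if the child later dies is defensible, because the event is physiological. For VFDs the event is liberation from the ventilator, and the endpoint is meant to combine time on the ventilator with survival. Under the carried-over rule, a child extubated on day 10 who dies on day 12 contributes exactly what a survivor extubated on day 10 contributes.

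An excess of such deaths in one arm would therefore leave no trace in the VFD hazard ratio. If one arm had the same total mortality but more of its deaths after extubation, it would look better with no gain in survival. This bears on the trial because Section 9.4.2 accepts that high ΔP could plausibly shorten ventilation and could also plausibly cause added harm. The results are also meant to inform a larger trial (Sections 6.4 and 9.4.4), where a VFD hazard ratio would naturally be read as a composite.

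**Working it through.** **The plan's own figure.** No figure is stated for VFDs. Section 6.4 gives 80% power and a type I error of 0.07 for the primary outcome, with 160 subjects, HR 1.5, prior precision 10 and success when P(HR > 1) exceeds 0.90. Take information I = events/4 and a success threshold of 1.2816 × √((I + 10)/I). The event count is not given. With an assumed 130 events:
- I = 32.5, and the threshold is 1.2816 × √(42.5/32.5) = 1.466.
- Type I error = 1 − Φ(1.466) = 0.071.
- Power = Φ(0.4055 × √32.5 − 1.466) = Φ(0.846) = 0.80.

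The stated figure reproduces, and the VFD rule does not touch it.

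**How many subjects.** Section 1.1 describes pediatric ARDS "with a mortality rate of 20% in the United States and 30% worldwide". At 20%, 0.20 × 160 = 32 deaths. If 10%, 25% or 50% of deaths follow extubation (assumed), 3.2, 8 or 16 children who died would be scored as liberated.

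**Two rules compared.** In both, a child who does not have the event stays in the risk set to day 28.
- Rule A (as written): only deaths before extubation count as never liberated.
- Rule B: every death by day 28 counts as never liberated.

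**Case 1: same share of deaths after extubation in both arms.** Assumptions: exponential extubation times with median 8 days, mortality 15% (low) versus 25% (high), large-sample Cox fit.

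| Share of deaths after extubation | HR, rule A | HR, rule B |
|---|---|---|
| 10% | 0.82 | 0.80 |
| 25% | 0.84 | 0.80 |
| 50% | 0.88 | 0.80 |

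The second decimal depends on when the extubations that precede death are assumed to occur.

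**Case 2: the timing of deaths differs by arm.** Assumptions: extubation at 3 days plus a Weibull time (shape 1.3, scale 9 days), 1,000,000 simulated subjects. Deaths are shown as percentage points before/after extubation.

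| Low arm | High arm | HR, rule A | HR, rule B |
|---|---|---|---|
| 15/5 | 25/5 | 0.78 | 0.79 |
| 15/5 | 15/10 | 1.00 | 0.89 |
| 15/5 | 15/15 | 1.00 | 0.79 |
| 15/5 | 10/10 | 1.14 | 1.00 |

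In the third row the mean difference in VFDs is −1.7 days when deaths score zero, and about 0 under rule A.

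**Rough hand check.** Let c be the proportion who can ever have the event. If event timing is the same in both arms, the ratio of cumulative subdistribution hazards runs from c₁/c₀ early to ln(1 − c₁)/ln(1 − c₀) late.
- Row 3, rule B: c = 0.80 (low) and 0.70 (high). The range is 0.70/0.80 = 0.88 to ln 0.30/ln 0.20 = 0.75, and 0.79 lies inside it. Under rule A both are 0.85, so the ratio is 1.
- Row 4, rule A: c = 0.85 and 0.90. The range is 0.90/0.85 = 1.06 to ln 0.10/ln 0.15 = 1.21, and 1.14 lies inside it. Under rule B both are 0.80, so the ratio is 1.

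**Size against the precision of the trial.** With an assumed 130 events the posterior SD of log HR is 1/√42.5 = 0.153, and the data carry weight 32.5/42.5 = 0.765.
- From 0.80 to 0.88: ln(0.88/0.80) × 0.765/0.153 = 0.48 SD.
- From 0.79 to 1.00: ln(1.00/0.79) × 0.765/0.153 = 1.18 SD.

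**The case against.** The strongest reply has four parts.

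- **The sentence on death after the event is worded for hypoxemia resolution and the primary outcome.** The VFD paragraph restates only death before the event. That is true, but the cross-reference has no exception and no other VFD rule is given. An analysis plan that follows the protocol would inherit the sentence.
- **Mortality has its own analyses.** It is a separate secondary endpoint with posterior probabilities (Sections 6.2 and 6.3.2), and death is a pre-specified safety outcome (Section 8.6). This stands: harm would not be hidden from the trial. It does not repair the VFD hazard ratio.
- **The size is assumed.** This also stands. If both arms have the same share of deaths after extubation, the shift is at most about half a posterior SD even at a 50% share, on an endpoint for which no power is claimed.
- **The composite label in Section 1.1 describes an adult trial result.** That is correct, but Sections 5.2 and 6.1 apply the same label when arguing for this trial's outcome.

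A reader might also infer stronger points that the documents do not support.
- The rule does not take mortality out of the endpoint altogether. Deaths before extubation are kept as competing events and lower the HR almost as much as under the full composite (0.78 against 0.79).
- An excess of deaths after extubation is ignored, not credited to the arm. Only a shift of deaths from before to after extubation makes an arm look better.
- The protocol does not say how re-intubation is treated, so nothing is stated wrongly there, and that definition may belong to the analysis plan.
- Nothing ranks VFDs above the other secondary endpoints.

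**Conclusion.** The point holds in a limited form. As written, the VFD hazard ratio is blind to deaths between extubation and day 28, which does not fit an endpoint the protocol calls a composite. This follows from a stated rule, not from a silence.

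The distortion is small if the share of deaths after extubation is the same in both arms. It is material if that share differs: a 10-point excess of late deaths can vanish, and an apparent benefit can arise at equal mortality. Equal mortality therefore does not by itself guarantee an unbiased VFD comparison. All these sizes rest on assumed death splits and extubation times, because the protocol gives neither. The primary outcome and the sample size are not affected.

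**What to change.** In the VFD paragraph of Section 6.3.2, add a sentence saying that for VFDs the rule on death after the event does not apply. It should state that any subject who dies by day 28, before or after extubation, stays in the risk set to day 28 as never liberated.

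The cost is one sentence of analysis wording, carried into the statistical analysis plan. It needs no new data, because 28-day mortality is already an endpoint and ventilation is recorded until it is discontinued.
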